14.2 EFFICACY VARIABLES

14.2.1.1 Analysis of Change from Baseline in Redness (Intent-to-treat Subjects)

Table 14.2.1.1 (Page 1 of 3)
Analysis of Change from Baseline in Redness
Intent-to-treat Subjects

Visit	Te (N=xx)	Tetrahydrozoline 0.05% Glycerin 0.40% (N=xx)	Tetrahydrozoline 0.05% Glycerin 0.20% Hypromellose 0.2% Polyethylene glycol 400 1.0 (N=xx)
Baseline			
n	XX	XX	XX
Mean	X.XX	x.xx	X.XX
S.D.	x.xxx	X.XXX	X.XXX
Median	X • XX	X.XX	X.XX
Min, Max	(x.xx,x.xx)	(x.xx,x.xx)	(x.xx,x.xx)
30 Seconds After First Application			
n	XX	XX	XX
Mean	X.XX	X.XX	X.XX
S.D.	X.XXX	X.XXX	X.XXX
Median	X.XX	X.XX	X.XX
Min,Max	(x.xx,x.xx)	(x.xx,x.xx)	(x.xx,x.xx)
Change from Baseline			
n	XX	XX	XX
Mean	X.XX	X.XX	X.XX
S.D.	X.XXX	X.XXX	X.XXX
Median	X.XX	X.XX	X.XX
Min,Max	(x.xx,x.xx)	(x.xx,x.xx)	(x.xx,x.xx)
Adjusted Mean	x.xx	x.xx	x.xx
s.e.	x.xxx	x.xxx	x.xxx
Pairwise Comparison vs			
Difference		x.xx	X.XX
s.e.		x.xxx	X.XXX
Between Treatment p-value [1]		0.xxx a	0.xxx a
95% CI		[x.xxx, x.xxxx]	[x.xxx, x.xxxx]

Ocular redness was assessed on a 5-point severity scale with 0.5 increments (0=none, 1=mild, 2=moderate, 3=severe, and 4=extremely severe).

^[1] P-values are based on mixed effect analysis of covariance model with treatment as factor, baseline value as a covariate.

Table 14.2.1.1 (Page 2 of 3) Analysis of Change from Baseline in Redness Intent-to-treat Subjects

Visit	Te (N=xx)	Tetrahydrozoline 0.05% Glycerin 0.40% (N=xx)	Tetrahydrozoline 0.05% Glycerin 0.20% Hypromellose 0.2% Polyethylene glycol 400 1.0% (N=xx)
60 Seconds After First Application			
n	XX	XX	XX
Mean	X.XX	X.XX	X.XX
S.D.	X.XXX	X.XXX	X.XXX
Median	X.XX	X.XX	X.XX
Min, Max	(x.xx,x.xx)	(x.xx,x.xx)	(x.xx,x.xx)
Change from Baseline			
n	XX	XX	XX
Mean	X.XX	X.XX	X.XX
S.D.	X.XXX	X.XXX	X.XXX
Median	X.XX	X.XX	X.XX
Min, Max	(x.xx,x.xx)	(x.xx,x.xx)	(x.xx,x.xx)
Adjusted Mean	x.xx	x.xx	x.xx
s.e.	x.xxx	X.XXX	x.xxx
Pairwise Comparison vs			
Difference		X.XX	X.XX
s.e.		x.xxx	X.XXX
Between Treatment p-value [1]		0.xxx a	0.xxx a
95% CI		[x.xxx, x.xxxx]	[x.xxx, x.xxxx]

Ocular redness was assessed on a 5-point severity scale with 0.5 increments (0=none, 1=mild, 2=moderate, 3=severe, and 4=extremely severe).

^[1] P-values are based on mixed effect analysis of covariance model with treatment as factor, baseline value as a covariate.

Table 14.2.1.1 (Page 3 of 3) Analysis of Change from Baseline in Redness Intent-to-treat Subjects

Visit	Te (N=xx)	Tetrahydrozoline 0.05% Glycerin 0.40% (N=xx)	Tetrahydrozoline 0.05% Glycerin 0.20% Hypromellose 0.2% Polyethylene glycol 400 1.0% (N=xx)
2 Minutes After First Application			
n	XX	XX	XX
Mean	X.XX	X.XX	X.XX
S.D.	x.xxx	X.XXX	x.xxx
Median	X.XX	X.XX	X.XX
Min, Max	(x.xx,x.xx)	(x.xx,x.xx)	(x.xx,x.xx)
Change from Baseline			
n	XX	XX	XX
Mean	X.XX	X.XX	X.XX
S.D.	X.XXX	X.XXX	X.XXX
Median	X.XX	X.XX	X.XX
Min, Max	(x.xx,x.xx)	(x.xx,x.xx)	(x.xx,x.xx)
Adjusted Mean	x.xx	x.xx	x.xx
s.e.	x.xxx	X.XXX	X.XXX
Pairwise Comparison vs			
Difference		X.XX	X.XX
s.e.		X.XXX	x.xxx
Between Treatment p-value [1]		0.xxx a	0.xxx a
95% CI		[x.xxx, x.xxxx]	[x.xxx, x.xxxx]

Ocular redness was assessed on a 5-point severity scale with 0.5 increments (0=none, 1=mild, 2=moderate, 3=severe, and 4=extremely severe)

^[1] P-values are based on mixed effect analysis of covariance model with treatment as factor, baseline value as a covariate.

14.2.1.2 Summary of Change from Baseline in Redness at 60 Seconds Subgroups (Intent-to-treat Subjects)

motorphidaesaline 0 05%

				Tetrahydrozoline 0.05% Glycerin 0.20%
			Tetrahydrozoline 0.05%	Hypromellose 0.2%
	Tet		Glycerin 0.40%	Polyethylene glycol 400 1.0%
Visit		(N=xx)	(N=xx)	(N=xx)
Baseline				
	n	XX	XX	XX
	Mean	X.XX	x.xx	x.xx
	S.D.	x.xxx	X.XXX	X.XXX
	Median	X.XX	x.xx	x.xx
	Min,Max	x.xx,x.xx	(x.xx,x.xx)	(x.xx,x.xx)
60 seconds Af	ter First Applicati	on		
	n	XX	XX	XX
	Mean	x.xx	X.XX	X.XX
	S.D.	x.xxx	X.XXX	X.XXX
	Median	x.xx	X.XX	X.XX
	Min,Max	x.xx,x.xx	(x.xx,x.xx)	(x.xx,x.xx)
Change from B	aseline			
	n	XX	XX	XX
	Mean	X.XX	X.XX	x.xx
	S.D.	x.xxx	X.XXX	X.XXX
	Median	x.xx	X.XX	X.XX
	Min, Max	x.xx,x.xx	(x.xx,x.xx)	(x.xx,x.xx)

Ocular redness was assessed on a 5-point severity scale with 0.5 increments (0=none, 1=mild, 2=moderate, 3=severe, and 4=extremely severe).

The tables for other subgroups will be similar as this.

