13.1. Sample Size Determination

This study is to demonstrate the therapeutic equivalence of the new formulation of to the current formulation based on the change from baseline in redness at 60 seconds after the initial eye drop. To determine the equivalence range, a meta-analysis was conducted. First, a sub-team was established and developed the search criterion and conducted a broad search of historical studies.

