1.1 Study Objectives

The objective of this study is to demonstrate the therapeutic equivalence of two investigational, over-the-counter (OTC) redness reliever eye drop formulations to an existing marketed OTC redness reliever eye drop in healthy adults with red eye.

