4 ENDPOINTS AND COVARIATES

4.1 Efficacy Endpoint(s)

The efficacy measurements include clinician assessment of ocular redness, subject reported ocular comfort and subject questionnaire.

The clinician assessment of redness will use a Redness will be evaluated in each eye at baseline (pre-
treatment prior to 1st product application), 30sec, 60sec, and 2 min after the first product
application.
The subject reported Ocular Comfort Assessment will be evaluated in each eye using
VAS scale at baseline, about 60 seconds after product application, and at 10 and
12 hours after the first product application. Subjects
will be shown the VAS scale and asked to select the point on the scale that corresponds to
their comfort level. The ocular comfort scale is included below:

A subject questionnaire will be administered to evaluate consumer sensory benefits. The questionnaire will be completed at Baseline, after the 2-minute ocular redness assessment in-clinic, and at home at the 10 (+15 minutes) and 12 (+15 minutes) hours after the first product application.

4.1.1 **Primary Efficacy Endpoint**

The primary efficacy endpoint is the change from baseline in redness at 60 seconds after the first application.

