6 STATISTICAL METHODOLOGY AND STATISTICAL ANALYSES

6.1 Statistical Hypotheses

The objective of this study is to demonstrate the equivalence of the test formulation to the control formulation. The statistical hypothesis is stated as

[figure not shown]

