6.2 Statistical Decision Rules

Not applicable.

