14.2.1.3 Analysis of Responder in Redness (Intent-to-treat Subjects)

Table 14.2.1.3 (Page 1 of 1)
Analysis of Responder [1] in Redness
Intent-to-treat Subjects

Visit	Te (N=xx)	Tetrahydrozoline 0.05% Glycerin 0.40% (N=xx)	Tetrahydrozoline 0.05% Glycerin 0.20% Hypromellose 0.2% Polyethylene glycol 400 1.0% (N=xx)
60 Seconds After First Application Responder Non-Responder Total	xx(xx.x%) xx(xx.xx%) xx(100%)	xx(xx.x%) xx(xx.xx%) xx(100%)	xx(xx.x%) xx(xx.xx%) xx(100%)
Adjusted Responder proportion	xx.x	xx.x	xx.x
Pairwise Comparison vs. Odds Ratio 95% CI Between Treatment p-value [2]		x.xx [x.xxx, x.xxxx] 0.xxx a	x.xx [x.xxx, x.xxxx] 0.xxx a

^[1] The responder is defined as the subject whose assessment score at 60 seconds after the initial eye drop is less than the assessment score at baseline.

^[2] P-values are from the GEE model with treatment as factor.

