14.2.2 Analysis of Change from Baseline in Ocular Comfort (Intent-to-treat Subjects)

Table 14.2.2(Page 1 of 3)
Analysis of Change from Baseline in Ocular Comfort
Intent-to-treat Subjects

J isit	Te (N=xx)	Tetrahydrozoline 0.05% Glycerin 0.40% (N=xx)	Tetrahydrozoline 0.05% Glycerin 0.20% Hypromellose 0.2% Polyethylene glycol 400 1.0% (N=xx)
60 Seconds After First Application			
n	XX	XX	XX
Mean	x.xx	X.XX	x.xx
S.D.	X.XXX	X.XXX	X.XXX
Median	X.XX	X.XX	X.XX
Min,Max	(x.xx,x.xx)	(x.xx,x.xx)	(x.xx,x.xx)
Change from Baseline			
n	XX	XX	XX
Mean	X.XX	X.XX	X.XX
S.D.	X.XXX	X.XXX	X.XXX
Median	X.XX	X.XX	X.XX
Min,Max	(x.xx,x.xx)	(x.xx,x.xx)	(x.xx,x.xx)
Adjusted Mean	X. XX	x.xx	X. XX
s.e.	x.xxx	x.xxx	X.XXX
Pairwise Comparison vs			
Difference		X.XX	X.XX
s.e.		X.XXX	X.XXX
Between Treatment p-value [1]		0.xxx a	0.xxx a
95% CI		[x.xxx, x.xxxx]	[x.xxx, x.xxxx]

Ocular comfort was assessed on an 11-point VAS scale (0-10) in which 0 = very uncomfortable and 10 = very comfortable. [1] P-values are based on mixed effect analysis of covariance model with treatment as factor, baseline value as a covariate.

The tables for 10hr after the first application and 12hr after the first application will be similar as this.

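### Does the primary equivalence table rest on a p-value that cannot show equivalence?

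*SAP*

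**What the plan says.** The aim is stated in SAP 1.1 ("The objective of this study is to demonstrate the therapeutic equivalence of two investigational") and again in SAP 6.1 ("The objective of this study is to demonstrate the equivalence of the test formulation to the control formulation"). SAP 4.1.1 fixes the endpoint: "The primary efficacy endpoint is the change from baseline in redness at 60 seconds after the first application". Protocol 13.1 says where the limits came from: "To determine the equivalence range, a meta-analysis was conducted". Their value is not shown in the public copy.

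The 60-second page of SAP Table 14.2.1.1 lists, for each test product against control, the difference in adjusted means, its standard error, a between-treatment p-value and a 95% CI. Footnote [1] explains the p-value: "P-values are based on mixed effect analysis of covariance model with treatment as factor, baseline value as a covariate". It mentions no equivalence limits, shifted null or pair of one-sided tests. The same row label is used for ocular comfort in Table 14.2.2 and for the responder odds ratio in Table 14.2.1.3, where the footnote reads "P-values are from the GEE model with treatment as factor".

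The section headed "6.2 Statistical Decision Rules" contains only the entry Not applicable.

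**The concern.** In an equivalence trial the null hypothesis is that the products differ by at least the margin. A p-value against zero difference tests something else. A large value may reflect only imprecision, and a small value may accompany a difference well inside the margin. The visible primary table carries such a p-value, or what looks like one, beside a CI. The section on decision rules does not say which of the two counts.

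If someone read p>0.05 as proof of equivalence, the stake would be a false claim about a product. If someone read p<0.05 as failure, a product that met the range could be reported as different. Unlike the hypothesis text, the 6.2 entry is complete and not blacked out, so it looks like an omission by the authors.

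**Working it through.** **What can be reproduced.** The synopsis plans 120 randomized to obtain 114 completers. 114 / 0.95 = 120, so the implied loss is 5%. The 114 itself cannot be rebuilt, because range, SD, alpha and power are not shown.

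**Precision of the primary comparison.** Each subject receives two of three products. With 114 completers there are 114 / 3 = 38 subjects per pair and 2 × 114 / 3 = 76 eyes per product. The incomplete-block efficiency is (1 − 1/2) / (1 − 1/3) = 0.75. Using within-subject information only, SE = SD × √(2 / (76 × 0.75)) = 0.1873 SD.

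| Assumed within-subject SD | SE | 95% CI half-width (1.96 × SE) |
|---|---|---|
| 0.3 | 0.056 | 0.110 |
| 0.5 | 0.094 | 0.184 |
| 0.7 | 0.131 | 0.257 |

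**How p-value and CI can part.** With an assumed margin of 0.3 and the CI taken as difference ± 1.96 × SE:

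- Difference 0.15, SE 0.05: p = 0.003, CI 0.052 to 0.248. Equivalent, although p<0.05.
- Difference 0.15, SE 0.12: p = 0.21, CI −0.085 to 0.385. Not shown equivalent, although p>0.05.

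**What a misreading would cost.** If the true difference equals the margin m, the chance of p>0.05 is Φ(1.96 − m/SE) − Φ(−1.96 − m/SE). For SD 0.3 / 0.5 / 0.7 this is 5.5 / 43 / 67% when m = 0.2, and 0.0 / 10.7 / 37% when m = 0.3. Requiring the 95% CI to lie inside the range holds the same error at 2.5% or less. The larger figures arise only if p>0.05 is taken as the criterion, and neither document says that.

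**Where the two readings would always agree.** Write h for the half-width. Then p<0.05 when the observed difference exceeds h in size, and the CI lies inside the range when it is below m − h. The two rules match only if m = 2h. With within-subject information and 111 df (228 − 114 − 2 − 1), h = 1.9816 × 0.1873 = 0.371 SD, so m = 0.742 SD. That is an upper limit. The footnote names a mixed model, and a random subject effect also recovers between-subject information. In units of the within-subject variance, with b the between-subject variance, the information is 114/4 + 38 / (4(1 + 2b)):

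- Between-eye correlation 0 (b = 0): 28.5 + 9.5 = 38, SE 0.162 SD, m = 0.64 SD.
- Correlation 0.5 (b = 1): 28.5 + 3.17 = 31.67, SE 0.178 SD, m = 0.70 SD.
- Correlation near 1: the second term vanishes, m = 0.74 SD.

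With a 90% CI for equivalence the corresponding points are 0.59, 0.65 and 0.68 SD. Away from such a point, the p-value and the CI will sometimes give different answers. How often they do is not an error rate, because only one of them tests equivalence.

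**Is the rule absent, or just not visible?** Protocol 13.1 breaks off after the meta-analysis search. Protocol 13.3.1 and 13.4 stop in mid-sentence, and the hypothesis in SAP 6.1 is not shown. SAP 4.4 sends the reader to 6.3 for details of the model, and SAP 6.4.2 sends the reader to 6.3.1 for the primary analysis. Yet the public 6.3 has one sentence on summary statistics, and 6.3.1 has only a subgroup paragraph. Text plainly stood there and was removed. These are the places where an equivalence rule would normally be written.

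**The case for a change.** The best case for a change does not depend on the blacked-out text. The 6.2 entry is complete as printed, and a confirmatory equivalence trial does have a decision rule. This SAP uses cross-references freely elsewhere, for example in 4.2, 4.4, 6.4.2 and 6.4.3, so a pointer would have been easy. If a correct rule stands in 6.1 or 6.3.1, Not applicable in 6.2 sits awkwardly beside it. Reading the p-value as a test of zero difference is also natural: there is one value per comparison, and the label is the same on the comfort and responder tables, where no equivalence range is visible. Confirming that the 95% level matches the planned alpha would be useful too. With assumed SD 0.5, margin 0.3 and no true difference, power is 78.6% with a 95% CI and 88.1% with a 90% CI.

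The drafting points stand: 6.2 is loosely worded, and the footnote does not name its null. They do not amount to a fault in the analysis. Printing an ordinary model p-value beside a CI is common and is not wrong in itself. The stated hypothesis is equivalence, and the CI is the printed statistic that addresses it. On the level, a 95% CI is the stricter choice compared with 90%, so it cannot inflate false claims of equivalence.

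**Conclusion.** The concern does not call for a change. The visible facts are as described, but the lack of a visible rule reflects the public copy, not a demonstrated gap in the plan. An analyst who follows the stated equivalence objective has the adjusted difference, its standard error and a two-sided 95% CI to set against the derived range, and would reach a sound conclusion whatever the p-value shows. A pointer in 6.2 or a fuller footnote would be a courtesy to readers and would change no data, model, estimate or conclusion.

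If the CI decides, the effect on the trial's result is nil. The false-claim rates above apply only to a misreading that the plan does not prescribe. They rest on assumed SDs of 0.3 to 0.7 and margins of 0.2 and 0.3. The verdict also assumes that the removed hypothesis and method text is consistent with the stated equivalence objective; nothing visible suggests otherwise.

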14.2.1.3 Analysis of Responder in Redness (Intent-to-treat Subjects)

Table 14.2.1.3 (Page 1 of 1)
Analysis of Responder [1] in Redness
Intent-to-treat Subjects

Visit	Te (N=xx)	Tetrahydrozoline 0.05% Glycerin 0.40% (N=xx)	Tetrahydrozoline 0.05% Glycerin 0.20% Hypromellose 0.2% Polyethylene glycol 400 1.0% (N=xx)
60 Seconds After First Application Responder Non-Responder Total	xx(xx.x%) xx(xx.xx%) xx(100%)	xx(xx.x%) xx(xx.xx%) xx(100%)	xx(xx.x%) xx(xx.xx%) xx(100%)
Adjusted Responder proportion	xx.x	xx.x	xx.x
Pairwise Comparison vs. Odds Ratio 95% CI Between Treatment p-value [2]		x.xx [x.xxx, x.xxxx] 0.xxx a	x.xx [x.xxx, x.xxxx] 0.xxx a

^[1] The responder is defined as the subject whose assessment score at 60 seconds after the initial eye drop is less than the assessment score at baseline.

^[2] P-values are from the GEE model with treatment as factor.

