4.1.2 Secondary Efficacy Endpoints

The secondary efficacy endpoints include:

- ➤ Change from baseline in redness at 30 seconds after the first application.
- > Change from baseline in redness at 2 minutes after the first application.
- ➤ Change from baseline in ocular comfort at approximately 60 seconds after the first application.
- ➤ Change from baseline in ocular comfort at approximately 10hr after the first application.
- ➤ Change from baseline in ocular comfort at approximately 12hr after the first application.

➤ Subject questionnaire at each collection time point. The Subject Questionnaire assesses consumer sensory benefits and includes 6 questions at baseline and 7 questions at 2 minutes, 10 hours, and 12 hours after first product application.

Change from baseline in both redness and ocular comfort will be calculated as the baseline score minus the post-baseline score.

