4.4 Covariates

For the analysis of ocular redness assessment and ocular comfort assessment, the corresponding baseline measurement will be used as the covariate in the analysis model, detailed information please refer section 6.3.

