6.3.1 Primary Endpoint

6.3.1.1 Subgroup analyses

The change from baseline in redness at 60 seconds after the initial eye drop will be summarized by treatment and each of the following

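### The responder GEE in SAP Table 14.2.1.3 names treatment only; adding the eye's baseline redness, with a marginal odds ratio from standardised proportions, is a small efficiency gain on a supportive table

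*SAP*

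**What the plan says.** Table 14.2.1.3 of the SAP plans responder counts per product, a row labelled "Adjusted Responder proportion", and an odds ratio with 95% CI and p-value for each new formulation against the marketed control. It prints no difference in proportions. Footnote [2] gives the model: "P-values are from the GEE model with treatment as factor". Footnote [1] gives the outcome: "The responder is defined as the subject whose assessment score at 60 seconds" is below the baseline score.

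SAP 4.4 says: "For the analysis of ocular redness assessment and ocular comfort assessment, the corresponding baseline measurement will be used as the covariate in the analysis model". The same sentence then sends the reader to section 6.3 for detail. The redness shell (Table 14.2.1.1) states: "P-values are based on mixed effect analysis of covariance model with treatment as factor, baseline value as a covariate"; the comfort shell (Table 14.2.2) has the same footnote.

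Under 6.3.1 the only visible text is the subgroup paragraph, which begins "The change from baseline in redness at 60 seconds after the initial eye drop will be summarized by treatment and each of the following". No model text is visible there, and this is treated as withheld, not absent. Responder status is neither the primary endpoint (SAP 4.1.1) nor in the list that opens "The secondary efficacy endpoints include" (SAP 4.1.2).

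**The concern.** The responder table uses the same baseline and 60-second scores as the redness table, yet it is the only modelled efficacy shell whose footnote leaves baseline out.

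Baseline is likely to predict this outcome. An eye responds if its later score falls below its own baseline score, and the scale is coarse: "Ocular redness was assessed on a 5-point severity scale with 0.5 increments". Reading error alone is then enough: an eye read too red at baseline is more likely to be read lower at 60 seconds, even if the true reduction has nothing to do with baseline. A treatment-only model leaves that predictable variation in the error.

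What is at stake is a little precision in a supportive table, and clarity about what the adjusted proportions are adjusted for.

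**Working it through.** **Inputs from the documents.** 120 subjects randomised for 114 completers (Protocol synopsis). Each subject receives 2 of 3 products, one per eye (SAP 1.2), so 114 × 2 / 3 = 76 eyes per product and 228 eyes in all. Redness is scored 0 to 4 in steps of 0.5 (Table 14.2.1.1). Entry requires mild/moderate redness in both eyes (Protocol 8.3.1, criterion 6).

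**Assumptions, because the documents give no figure.** Baseline 1 to 2 or 1 to 2.5; latent correlation between eyes 0.5 to 0.9; subject random-intercept SD 1; response rate 44 to 85%; baseline slope γ from 0 to 1.5 log-odds per grade.

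**Models compared.**
- Unadjusted: logit p = α + β(product).
- Adjusted: logit p = α + β(product) + γ × (baseline of the eye). The standardised proportion for product k is the mean, over the observed baselines x of all analysed eyes, of expit(α + β_k + γx). Marginal odds ratio = [p_k/(1 − p_k)] / [p_control/(1 − p_control)].

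Both are GEE clustered on subject with robust variance. There is no planned figure to reproduce, since no responder rate or power for this table is visible.

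**Variance ratio, unadjusted over standardised, for the difference between two products' responder proportions** (4,000 simulated trials per setting):

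| Slope per grade | Independence | Exchangeable |
|---|---|---|
| 0 | 0.993–0.998 | 0.993–1.000 |
| 0.5 | 1.002–1.010 | 1.000–1.007 |
| 1.0 | 1.014–1.038 | 1.010–1.032 |
| 1.5 | 1.024–1.087 | 1.017–1.076 |

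A separate run with independence GEE gave 0.99 at slope 0, 1.01–1.02 at 0.5 and 1.08–1.09 at 1.5. The difference is not printed, but the marginal odds ratio is a smooth function of the same two proportions, so by the delta method a similar gain carries over to it.

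**In plainer units.** A ratio of 1.09 cuts the standard error by 1 − 1/√1.09 = 4.2%, and 114 × 0.09 ≈ 10, so it is like having 10 more completers. A ratio of 0.99 costs about 1 completer (114 × 0.01 ≈ 1).

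**Reading-error model.** The true reduction is unrelated to baseline, reading-error SD is 0.1 to 0.4 grade and scores are rounded to 0.5. The fitted slope is 0.5 to 2.0 per grade and the variance ratio 1.01 to 1.17. The separate run gave 1.03 to 1.09.

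**Validity.** With no product effect, rejection at 5% was 3.8 to 5.8% unadjusted and 3.9 to 5.9% adjusted. Standardised proportions are equal exactly when β = 0, so the marginal comparison tests the same null.

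**Which odds ratio to print** (product effect −1):

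| Slope | Unadjusted | Conditional on baseline | Marginal, from standardised proportions |
|---|---|---|---|
| 0.5 | 0.438 | 0.430 | 0.437 |
| 1.5 | 0.467 | 0.423 | 0.467 |

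The standard error of the conditional log odds ratio is about 1% larger than the unadjusted one at slope 0.5 and 7–8% larger at 1.5. A further run with exchangeable GEE put the widening of the interval at 1.4–1.5% and 8–9%. The marginal odds ratio is unchanged by the adjustment (−0.759 against −0.759 on the log scale at slope 1.5).

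**Why standardise and not predict at the mean baseline.** With an assumed slope of 3.0, chosen to make the effect visible, the observed control proportion was 0.667. Prediction at mean baseline gave 0.704; standardisation gave 0.669.

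**The case against.** A reader might infer that the shell contradicts SAP 4.4. The documents do not support that. SAP 4.4 speaks of one analysis model and refers to 6.3, whose responder text cannot be seen. It can be read as covering only the change-score ANCOVA. The responder outcome is binary, uses a different method and has its own footnote, and shell footnotes are often abbreviated.

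A reader might also take the row label "Adjusted Responder proportion" as proof that a covariate was forgotten. It is not. In an incomplete block design with exchangeable working correlation, treatment-only GEE proportions already differ from the raw ones, by about 0.005 on average, so the label can be meaningful without baseline.

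The strongest objection to acting concerns the odds ratio. Simply adding baseline would replace a marginal odds ratio with a conditional one, widen the printed interval, and set it beside proportions that no longer reproduce it. This objection stands, and it is why the fix takes the odds ratio from the standardised proportions.

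It is also true that the gain may be nil. For the product coefficient at effect −1 and slope 0.5, rejection was 73.7% unadjusted against 74.1% adjusted (independence) and 74.8% against 74.7% (exchangeable). At slope 1.5 it was 67.0% against 70.5%, and 69.2% against 71.3%.

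**Conclusion.** This is a small efficiency improvement, not an error. The treatment-only GEE is a valid comparison, and the primary equivalence conclusion does not depend on this table. Baseline is a sensible covariate because it is already collected, is used in the sibling models and enters the outcome definition.

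The size is a variance ratio of about 0.99 to 1.09 for slopes of 0 to 1.5 per grade, and up to 1.17 in the most favourable reading-error setting. All slopes, error sizes and correlations behind these figures are assumptions. A reader might infer bias or an inflated error rate from the missing covariate; the null rejection rates, close to 5% with and without it, show neither.

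**What to change.** Replace footnote [2] of Table 14.2.1.3 with:

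*GEE model with treatment as factor and the eye's baseline redness as a covariate; adjusted responder proportions are standardised over the observed baseline redness of all analysed eyes, and the odds ratio, 95% CI and p-value are the marginal ones computed from these proportions with subject-clustered robust (delta-method or bootstrap) variance.*

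Align 6.3.1 so that text and shell describe one model. Make the change before database lock and release of the randomization, the point by which Protocol section 13 requires the SAP to be final. In the simulations, adding baseline moved the difference between two products' proportions by 0.4 to 1.8 percentage points on average for slopes 0.5 to 1.5, so the choice should not be left to programming.

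Accompanying wording edit: in footnote [1], 'the subject whose' should read 'the eye whose'. Each subject has two eyes on different products, and Listing 16.2.6.1 already records response per eye.

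Cost: no new data, one standardisation step in the program, two footnote edits, and under 1% in variance if baseline turns out to have no effect.
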